NIMP	Non- Investigational Medicinal Product
PI	Principal Investigator
PIS	Participant Information Sheet
QA	Quality Assurance
QC	Quality Control
QP	Qualified Person for release of trial drug
RCT	Randomised Control Trial
REC	Research Ethics Committee
SAR	Serious Adverse Reaction

SAE	Serious Adverse Event
SDV	Source Document Verification
SOP	Standard Operating Procedure
SmPC	Summary of Product Characteristics
SSA	Site Specific Assessment
SSAR	Suspected Serious Adverse Reaction
SUSAR	Suspected Unexpected Serious Adverse Reaction
TMG	Trial Management Group
TSC	Trial Steering Committee

2 Study personnel

- Principal Investigator (PI):** [name]
E-mail: [contact]
[contact] [name]
[contact]
- Statistician:** [name]
E-mail: [contact]
[contact] [name]
- Medical Expert:** [name]
E-mail: [contact]
[contact] [name]
[contact]
- Pharmacy:** Royal Brompton and Harefield NHS Foundation Trust
E-mail: [contact]
[contact] [name]
[contact]
- Co-Investigators:**
- [name],
Email: [contact]
[contact]
- [name]
Email: [contact]
- [name],
Email: [contact]
[contact]
- [name]
Email: [contact]
[contact]
- [name]
Email: [contact]
[contact]
- [name],
Email: [contact]
[contact]
- [name] [name],
Email: [contact]

3 Study synopsis

Full study title:	Randomized, controlled crossover trial to evaluate the effects of Ambulatory Oxygen on health status in patients with Fibrotic Lung Disease (FLD).
Short study title:	Ambulatory Oxygen in Fibrotic Lung Disease (FLD)
Study R&D number:	2013OE0058B
Study drug:	Medical Oxygen
Chief Investigator:	[name]
Study centres/sites:	
 1. Royal Brompton Hospital ILDU 2. Respiratory Medicine Aintree Hospital 3. Respiratory Medicine King's College Hospital (KCL)
Study duration:	30 months
Clinical phase:	Phase IV
Primary Objective:	
 • Change in health status (as assessed by K-BILD questionnaire)
Secondary Objective:	
 • Dyspnoea scores, global patient assessment, monitored and patient-recorded activity parameters, Quality of Life (QoL) scores. • In a subgroup of patients, semi-structured interviews at the end of the four-week period will be conducted to evaluate patients' and carers' experiences with ambulatory oxygen and trial participation.
Study population:	Patients with Fibrotic Lung Disease (FLD), including the idiopathic interstitial pneumonias and fibrotic hypersensitivity pneumonitis.
Methodology:	Four-week randomized crossover trial of ambulatory oxygen for use during physical activity.
Eligibility criteria:	
Inclusion criteria:
 
 1. IPF or any other Fibrotic Lung Disease (FLD) 2. patients aged 18 – 99 yrs 3. Desaturation \leq 88% on a 6MWT on room air 4. Stable respiratory symptoms (no changes in medications and no chest infections) in the 4 weeks preceding the randomisation including the run in period
	
Exclusion criteria:
 
 1. Patients meeting criteria for long term oxygen therapy, SaO₂ at rest on room air < 94% 2. Patients expected to change treatment during the course of the study 3. Significant locomotor or communication difficulties 4. Patients with sarcoidosis or connective tissue disease

	
affecting the musculoskeletal system
 
 5. Current smokers 6. Pregnancy 7. History of symptomatic ischaemic cardiac disease (exertion-induced chest pain) 8. Anaemia, Hb < 9g/dl
Study drugs, Dose and Mode of Administration:	

Medical oxygen (Oxygen Ph. Eur. 100%) PL 15929/0005, obtained through the Home Oxygen Order Form (HOOF), supplied by Air Liquide (for the areas of South/North London, North West, East Midlands and South West), or by BOC (for the areas of Eastern England, North East) or by Dolby Vivisol (for the areas of South Central, South East Coast) or by Baywater Healthcare (for the areas of Yorkshire & Humberside, West Midlands, Wales) as per standard clinical practice. The light-weight portable oxygen gas cylinders will be used across sites to standardise mode of delivery.
 
The study will consist of a four week randomized crossover trial of ambulatory oxygen for use during physical activity. Patients meeting inclusion criteria and deemed clinically stable at the end of the run in period, will be assigned in random order to two weeks on ambulatory oxygen or not. Oxygen flow rates will be determined on the basis of the entry 6MWT on O₂, so as to maintain oxygen saturation ≥ 90% for at least half of the 6MWT duration, where possible. Modification of the flow rate is not anticipated for the duration of the study.
	
Duration of Treatment:	Two weeks
Criteria for evaluation:	
Primary outcome variable:
 
 • change in the total “health status” score as assessed by the K-BILD questionnaire
	
Secondary outcome variables:
 
 • dyspnoea scores, global patient assessment, monitored and patient-recorded activity parameters, Quality of Life (QoL) scores.

4 Introduction

4.1 Background

Fibrotic Lung Diseases (FLDs) are chronic and progressive conditions resulting in substantial morbidity and mortality. The cardinal symptom of all fibrotic Interstitial Lung Diseases (ILDs) is shortness of breath. Although initially present only on strenuous activities, this unfortunately progresses until even routine activities of daily living become severely limited. This has a devastating impact on Quality of Life (QOL). Measures aimed at improving respiratory symptoms, social interactions and mobility are key to maintaining acceptable QOL standards for as long as possible. Patients with ILD can experience marked desaturation on exercise (1; 2). Exercise limitation in ILD is thought to be caused by multiple factors, including oxygen diffusion limitation, ventilation/perfusion mismatch and low mixed venous oxygen tension, although the pulmonary vasculature is the main limiting factor (3). In keeping with this, desaturation on exercise is significantly associated with pulmonary hypertension, and may contribute to pulmonary hypertension at rest (4). As pulmonary fibrosis advances, exertional breathlessness is triggered by ever decreasing activity levels. Eventually basic tasks, such as washing and dressing, become a challenge.

An improved understanding of the effects of ambulatory oxygen in patients with ILD should lead to significant benefits in terms of exercise performance, reduced symptoms of breathlessness and improved mobility in daily life. Currently, there is no standardised approach to the assessment and prescription of ambulatory oxygen in ILD patients. In many centres, the need for ambulatory oxygen in ILD is not routinely assessed. Although several centres including the centres participating to this study, routinely prescribe ambulatory oxygen to ILD patients with desaturation on exercise, there are no guidelines to direct ambulatory oxygen prescription, and no studies to indicate its benefits and drawbacks in patients with ILD.

4.2 Investigational Medicinal Products (IMPs)

Name of the study IMP: Medical Oxygen

Qualitative and Quantitative Composition: Oxygen Ph. Eur. 100%

Pharmaceutical Form: Inhalation Gas

Medical Oxygen used in this study is manufactured by Air Liquide Ltd., UK. Manufacturing Authorization, PL 15929/005 was issued on 04th February 1998 and renewed on 17th April 2003.

4.3 Pre-clinical data

There are very few studies investigating the physiological effects of supplemental oxygen on exercise capacity in ILD. Bye *et al* observed improvement in maximal oxygen uptake, maximal exercise workload and exercise duration in 16 patients with ILD breathing supplemental oxygen during incremental exercise (5).

4.4 Clinical data

We have recently completed a retrospective assessment showing that supplementary ambulatory oxygen improves the performance of a Six Minute Walk Test (6MWT) in patients with ILD (6). Frank and co-authors reported that further up titration of ambulatory oxygen in order to maintain saturation value above 90% or reach a 6L/min flow rate during 6MWT seemed to improve exercise capacity in IPF, as measured by a 6MWT, even in patients already using oxygen at home (7). Although the results of these retrospective reviews are highly encouraging, a prospective standardised study is needed to assess the impact of ambulatory oxygen on ILD patients' day to day Quality of Life (QoL).

4.5 Study Rationale and risk/benefit analysis

There are no prospective studies assessing whether ambulatory oxygen provides benefit to patients with ILD and no guidelines for use of oxygen in diffuse lung diseases. In particular, NICE guidelines for oxygen use only address COPD: (<http://guidance.nice.org.uk/CG101>), a disease which markedly differs from IPF or other ILDs, while the BTS document on oxygen use, only briefly touches on ambulatory oxygen (<http://www.library.nhs.uk/GuidelinesFinder/ViewResource.aspx?resID=111561>), and gives no specific guidance on its use in any of the Interstitial Lung Diseases (ILD). Specifically, there are no studies investigating the effects of ambulatory oxygen on day-to-day life in patients with Fibrotic Lung Disease (FLD), or assessing whether oxygen-induced improvements in 6MWT performance predict response to supplemental oxygen during activities of daily living, and an overall improvement in health status.

We have therefore planned a prospective study to assess whether ambulatory oxygen increases the health status of patients with Fibrotic Lung Disease (FLD) who experience oxygen desaturation on a 6MWT. The proposed project is the first of its kind in ILD, and addresses an under-researched area in urgent need of study. The study has the potential to lead to significant advances in the treatment and the understanding of exercise limitation in patients with ILD, and will represent an essential step towards the development of guidelines on oxygen use in ILD.

Currently, the prescription of ambulatory oxygen in ILD varies widely across the UK, with many respiratory centres only prescribing supplemental oxygen when the patient is hypoxic at rest. A 6MWT in ILD patients does not form part of the routine work up of ILD patients outside of specialised centres. This study aims to assess whether individuals with Fibrotic Lung Disease (FLD) whose SaO₂ falls \leq 88% on a 6MWT benefit from the use of ambulatory oxygen in their daily lives, by assessing changes in health status.

The risks associated with the use of ambulatory oxygen are limited and highly manageable. As patients selected for the study will not be hypoxic at rest, and therefore will not be on long term oxygen, the risk of inappropriately low oxygen concentrations will not apply. The main reason for performing this study is to assess whether using ambulatory oxygen in ILD patients who desaturate on exercise, is associated with significant subjective benefits. One of the potential risks is that the lack of supplemental ambulatory oxygen during the two trial weeks off ambulatory oxygen could be associated with worse symptoms of breathlessness and increased fatigue. However, it is precisely because this is not yet known that the study is justified.

There is a theoretical risk of inappropriately high oxygen flows causing hypercapnia. However, this is mainly an issue in patients with COPD, where type II respiratory failure is relatively frequent. Conversely, in Fibrotic Lung Diseases (FLD), hypercapnia usually only occurs during the final stages of Fibrotic Lung Disease (FLD), when patients are hypoxic at rest and require continuous supplemental oxygen, a subgroup which will be excluded in this study.

Ambulatory oxygen will be provided through nasal cannula.

4.6 Management of potential study risks

In ILD patients who desaturate to $\leq 88\%$ on a 6MWT, the physicians in the centres participating to this study (RBH, Aintree, King's) would be offering and prescribing ambulatory oxygen regardless of participation to the study, as part of local standard care. However, as stated previously, there are no national standards or guidelines to aid in the prescription of ambulatory oxygen in ILD patients in the UK. Many other centres do not routinely assess the need for ambulatory oxygen in lung fibrosis, and there has not yet been a study to show that it is effective. Therefore, patients will be asked to spend two of the four weeks not using ambulatory oxygen. This will not be different to what patients would have been doing just prior to the assessment (*i.e.* not using ambulatory oxygen). Although not using ambulatory oxygen could lead to increased breathlessness or reduced levels of activity compared to the two weeks on ambulatory oxygen, this is justified by the need for a study to assess the effectiveness of ambulatory oxygen.

The study team will contact patients by telephone during both the two weeks on oxygen and the two weeks on air. Should the patients struggle with breathlessness in the two weeks on air and request oxygen cylinders, this would be arranged and taken into account in the analysis of the study results. Patients who experience problems during the two weeks on air and require using oxygen will be asked to add this information to their patient diaries. The information will subsequently be recorded in the CRFs and the database.

Ambulatory oxygen is associated with a potential fire hazard. However, this is well known and routinely managed in the context of the existing ambulatory oxygen service. In this regard, all patients will be educated with regards to the potential fire hazards of supplemental oxygen, as routinely done by our oxygen services, as part of the standard prescription of ambulatory oxygen by our services. In view of the potential fire hazard, current smokers will be excluded.

There is a theoretical risk of hypercapnia, which is truly minimal, as this only occurs in a subgroup of patients during the terminal stages of fibrotic ILD, when hypoxia is present also at rest, and these patients will be excluded from the study.

5 Study objectives

5.1 Primary objective

The main aim of this project is to establish whether ambulatory oxygen in patients with fibrotic ILD whose oxygen saturation falls $\leq 88\%$ on a 6MWT, leads to a significant improvement in their health status. The core of the project will be randomised, controlled

trial ambulatory oxygen used at home at an optimal flow rate determined by titration at screening visit and administered for a two-week period, compared to two weeks off oxygen.

5.2 Secondary objective

Secondary outcomes will include dyspnoea scores (including the University of California San Diego Shortness of Breath Questionnaire hereafter referred to as the Shortness of Breath Questionnaire), global patient assessment, monitored and patient-recorded activity parameters, and Quality of Life (QOL) scores assessed by the King's Brief Interstitial Lung Disease Questionnaire (K-BILD) and the St George's Respiratory Questionnaires, as well as the Hospital Anxiety and Depression Scale. We also aim to assess whether the improvement in 6MWT performance induced by portable oxygen can predict benefit of ambulatory oxygen in day to day living.

In addition, semi-structured interviews at the end of the four-week period in a subgroup of 20 patients will be conducted to evaluate patients' and carers' experiences regarding the use of ambulatory oxygen and trial participation.

6 Trial design

6.1 Overall design

The planned non-commercial study is a randomised, controlled crossover trial of ambulatory oxygen against no ambulatory oxygen over a four week period (two weeks on ambulatory oxygen and two weeks on air), to evaluate the effects of ambulatory oxygen on health status in patients with ILD. A short crossover study in this context has many advantages, since ambulatory oxygen has immediate effect, with no wash-out period needed after use.

At the start of the trial, the effects of ambulatory oxygen on 6 Minute Walk Test (6MWT) performances will be evaluated on oxygen and on air-filled canisters, with the patient blind to the contents of the canister, to assess whether oxygen-induced improvements in 6MWT parameters can predict its effectiveness in day to day life. The 6MWT is a well-established and highly reproducible test validated in ILD patients (8; 9), with significant prognostic implications (10).

The study design does not include a placebo arm because:

- a) The intervention is a combination of possible benefits from oxygen and the disadvantage of canister weight. These cannot be separated. Placebo control is impossible because there is no means of providing placebo weight. Attempts to control solely for oxygen use without taking canister weight into account are clinically meaningless. In a recent COPD study, cylinder weight was reported as a barrier to use by 93% of study participants (11).
- b) A positive result against an air-filled canister arm would be clinically uninterpretable. This is a study design in which the 'placebo' would be actively harmful to study participants. Carriage of an air-filled cylinder would be expected to lead to earlier desaturation and reduced exercise tolerance. Such a design would not inform the real life comparison between oxygen plus cylinder and no intervention.

- c) All this aside, blinding is legally impossible (UK health and safety regulations **require** that oxygen cylinders for home use must be clearly labelled).

It should also be stressed that objective measures of change are evaluated as secondary end-points: we expect to explore correlations between these variables and the primary end-point to exclude the possibility that an observed treatment benefit on the primary end-point might be confounded by a placebo effect.

6.1.1 Target population and screening:

Patients with a diagnosis of IPF, or with another fibrotic ILD (including fibrotic non-specific interstitial pneumonitis, fibrotic organising pneumonia and fibrotic hypersensitivity pneumonitis) according to established guidelines, (12; 13), whose oxygen saturation (SaO₂) at rest on room air is $\geq 94\%$ and falls $\leq 88\%$ on a baseline 6MWT will attend Visit 1 (Screening visit Week (- 2)) to undergo initial screening..

We plan to obtain informed consent and screen patients during their routine outpatient/inpatient assessment. As part of routine clinical care, all patients will undergo: past and current medical history, current concomitant medications, demographics, routine blood tests including BNP, echocardiogram, physical assessment, including oxygen saturation on room air (RA), and a six Minute Walk Test (6MWT). Historical evidence for the investigations will be acceptable as outlined in Section 10.2 of the study protocol.

Patient of childbearing potential will be tested for pregnancy during the screening visit.

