6.1.2 Two weeks Run in period

Following the initial screening visit (Visit 1) subjects consented for the study will enter a two week run in period. There should be no changes to treatment or lifestyle in this period.

- Subjects who fail to meet the eligibility criteria at the end of the run-in period will be withdrawn from the study.
- Subjects who meet eligibility criteria and are deemed stable at the end of the run-in period will be assigned in random order to two weeks on ambulatory oxygen or no treatment for two weeks during the baseline visit.

6.1.3 Baseline Assessments – Visit 2 in Week 0

After the two weeks 'run in period' patients will return to the clinic to attend the baseline visit (study Visit 2 in Week 0).

Patient will be asked to complete the K-BILD (14) questionnaire in addition to other questionnaires (the Shortness of Breath Questionnaire (SOBQ (15)), St George's Respiratory Questionnaire (SGRQ) (16), Hospital Anxiety and Depression Scale (HDAS)(17,18)), and to perform two 6MWTs, one on oxygen and one on air-filled canisters at the flow rate identified during the screening visit, in random order, with a rest of at least 30 minutes between tests. The patient will be blind to the content of the canisters.

Measured parameters will include 6-minute walk distance, oxygen saturation and heart rate measured continuously (WristOx2™ model 3150), Borg dyspnoea and fatigue score before and at the end of the test, time to recovery of heart rate, oxygen saturation, Borg dyspnoea and fatigue. These parameters will be related to any changes in the primary and secondary outcome variables in the current trial, to identify any baseline predictors of responsiveness.

Only patients with stable respiratory symptoms at baseline visit (no changes in medications and no chest infections during the four weeks before the baseline visit including the run in period) will be randomized into the study as outlined in Section 9.2.

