17.2 Endpoints

17.2.1 *Primary endpoints*

The primary endpoint will be the change in health status, as measured by the K-BILD questionnaire (14). It is a continuous variable.

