17.2.2 Secondary endpoints

- a) Dyspnoea scores as assessed by the San Diego shortness of breath questionnaire (15)
- b) Global assessment of change in walking ability and exertional breathlessness as better, the same or worse
- c) Quality of life as assessed by SGRO (16) and the hospital anxiety and depression score (18)
- d) Sense wear activity monitor measures of daily number of steps walked, daily expenditure and time spent at different levels of activity
- e) Continuous oxygen saturation for 48 hours at weekly intervals

- f) Individual questions specifically related to activity from both the K-BILD and the SOBQ questionnaires

All of the above are continuous variable and will be analysed as such at least in the first instance. However, categorical analysis will also be performed, when appropriate on reviewing the distribution of the data.

Qualitative assessment of the impact of ambulatory oxygen. With regards to the qualitative arm of this study, we plan to investigate patients' and their carers' personal perspectives on how the ambulatory oxygen has affected their day to day life by conducting semi-structured open-ended interviews in a subset of 20 patients and their carers at the end of the study. Based on the information we gained from informal conversations with ILD patients already using ambulatory oxygen, a topic guide will address a series of issues identified as important, including practical barriers to optimal oxygen usage, practical, social and psychological difficulties encountered, concerns about dependency, and views on the information required prior to ambulatory oxygen prescription. The interviews will also explore patients' (and carers') experience of participating in the trial and recruited at RBH in order to inform the definitive multi-centre trial. Field notes will be written after each interview to aid reflexive analytical processes (25). Individual feed-back on how the system and the service could be improved will assess how the needs of patients and their future involvement can be incorporated into the design of more patient centred devices.

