17.5 Randomisation

Simple block method randomization will be performed to determine the order of treatment. As the study is un-blinded, varying block sizes will not be required.

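### Correlating objective measures with K-BILD cannot exclude a placebo effect in this open-label trial, so the claim in section 6.1 should be withdrawn

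*Protocol*

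**What the plan says.** Protocol section 6.1 sets out the case for an uncontrolled-for-placebo comparison under the lead-in "The study design does not include a placebo arm because": cylinder weight is part of the intervention, an air-cylinder arm would not answer the real-life question, and home blinding is legally impossible. It then stresses that objective measures are assessed as secondary endpoints and continues: "we expect to explore correlations between these variables and the primary end-point to exclude the possibility that an observed treatment benefit" on that endpoint "might be confounded by a placebo effect".

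Four other statements bear on this:

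- Section 17.2.1: "The primary endpoint will be the change in health status, as measured by the K-BILD questionnaire". Section 10.1 describes this as the patient's own rating of the previous two weeks.
- Section 17.5: "As the study is un-blinded, varying block sizes will not be required".
- Section 17.2.2 lists the objective measures as "Sense wear activity monitor measures of daily number of steps walked, daily expenditure and time spent at different levels of activity", together with 48-hour oximetry.
- Section 6.1.3, on the two baseline walk tests with oxygen and with air: "The patient will be blind to the content of the canisters". Section 9.3 adds that the investigator is not blind in these tests.

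Sections 17.4.2 and 17.4.3 specify paired tests and regression or mixed models. Neither describes the correlation analysis nor says what result would count as excluding a placebo effect.

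**The concern.** The sentence promises an inference that the named analysis cannot support. Whether a K-BILD gain is due to oxygen or to expectation is a question about the mean on-minus-off difference. A correlation across patients describes how individual differences vary together, after the means have been removed.

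Expectation is a realistic concern here. Patients know which period they are in. The participating centres would offer ambulatory oxygen to these patients anyway (section 4.6), and everyone is offered it afterwards (section 13.6).

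At stake is how a positive result may be described. A report relying on this sentence could present a significant correlation as showing that the K-BILD benefit is free of placebo effect, or could treat the absence of a correlation as casting doubt on a genuine benefit. Section 4.5 expects the study to feed into guidelines on oxygen use, so the strength of the claim matters.

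**Working it through.** **1. The plan's own figure.** The disputed sentence carries no number. The nearest is the sample size in section 17.3.1: difference 8, SD 20, 90% power, 5% significance (two-sided assumed), 15% dropout, 80 patients. I take 20 as the SD of the within-patient difference.

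- Normal approximation: n = (20 × (1.960 + 1.282) / 8)² = 65.7, so 66; 66 / 0.85 = 77.6, so 78.
- Exact paired t: n = 68 (power 0.902); 68 / 0.85 = 80, as stated.
- IPF subgroup, n = 56: power 0.837, against the stated 84%.

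The figures reproduce. I use 68 completers below.

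**2. The algebra.** The protocol does not say which quantities will be correlated; I assume on-minus-off differences. For patient i, let the K-BILD difference be D_i = c + e_i, where c is the shift common to all patients (oxygen, expectation or both), and let O_i be the difference in the objective measure. Pearson's r uses D_i minus its mean, so c cancels: corr(c + e, O) = corr(e, O). Ranks are also unchanged, so Spearman's coefficient behaves the same way. The correlation carries no information on whether c comes from oxygen or expectation. If the two periods were pooled instead, the shift could move r, but by an amount that depends on its size and not its cause.

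**3. Illustration.** 20,000 simulated trials per setting, n = 68, mean K-BILD difference 8, SD 20, an objective measure with no mean effect, and an assumed correlation ρ between the two differences. No document gives a value for ρ. Entries are proportions of trials.

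| ρ | r significantly positive: shift all placebo | r significantly positive: shift all oxygen | K-BILD and r both significant: shift all placebo |
|---|---|---|---|
| 0 | 0.024 | 0.023 | 0.021 |
| 0.2 | 0.378 | 0.374 | 0.341 |
| 0.3 | 0.708 | 0.716 | 0.634 |
| 0.4 | 0.933 | 0.928 | 0.840 |
| 0.5 | 0.993 | 0.994 | 0.900 |

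The placebo and oxygen columns differ only by simulation error, as step 2 requires. The proportions are simply the power of a correlation test. By Fisher's z, power ≈ Φ(√(68 − 3) × atanh ρ − 1.96). For ρ = 0.3 this is Φ(8.062 × 0.3095 − 1.96) = Φ(0.54) = 0.70.

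**4. Both directions.**

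- *A correlation without oxygen benefit.* Steps and time at activity levels are voluntary. A hopeful patient may do more and also rate health better, which gives ρ > 0 with no oxygen effect. Ordinary fluctuation in health can do the same.
- *Oxygen benefit without a correlation.* A true 8-point gain, equal in all patients, adds nothing to the covariance. With ρ = 0 a significant positive r appears in about 2% of trials, essentially the nominal 2.5%.

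**5. Oximetry.** Saturation is less directly open to expectation than steps. Hopeful patients may still use cylinders more, which could link saturation to K-BILD, and the invariance in step 2 applies whichever measure is used.

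**The case against.** The best reply is that this is one phrase in a design-rationale paragraph. The protocol only expects to explore these correlations. It sets no test, threshold or decision rule, and the details could be left to an analysis plan. That stands as a limit on the importance of the point. It does not rescue the phrase, because the conclusion promised is exclusion, and no specification of a correlation could provide it.

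A reader might infer that the correlation is the protocol's only answer to expectation bias. The text does not support that. The same sentence first points to the objective secondary endpoints themselves, and section 6.1 gives a pragmatic argument for comparing oxygen plus cylinder with no intervention. That argument is not disputed here. Section 17.4.3 already provides paired on-versus-off comparisons of the continuous secondary measures, so much of the better evidence is planned.

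It is also fair to say that the activity argument in step 4 does not carry over directly to saturation. The algebra in step 2 does.

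Finally, the patient-blind walk tests should not be oversold as a substitute. The investigator knows the canister content, the comparator is an air-filled canister that section 6.1 itself considers uninformative for the real-life question, and the tests show an acute effect only. Section 6.1.3 relates them to later outcomes in order to find predictors of response.

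**Conclusion.** The point holds as a correction to one inferential claim. Correlations between objective measures and K-BILD cannot exclude a placebo contribution to an open-label, patient-reported benefit, and nothing elsewhere in the protocol corrects the statement.

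The core is algebraic and, for on-minus-off differences, needs no assumption about the size of any correlation. The percentages do rest on assumed values of ρ, on 68 completers, on an SD of 20 and on normality. A reader might take 38%, 71% or 93% as the chance of a wrong conclusion in this trial. They are not: they show what a correlation test does at each assumed ρ.

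A reader might also infer that the primary result is compromised. It is not: the primary test, the sample size and the data collected do not depend on this analysis. What changes is how a K-BILD benefit may be interpreted and reported.

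**What to change.** Amend section 6.1, and carry the same wording into the analysis plan:

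- Delete the claim that correlations exclude a placebo effect. Keep any correlations as descriptive.
- Name the on-minus-off differences in the Sensewear measures and 48-hour saturation, already covered by section 17.4.3, as the supportive objective evidence. Report them with 95% confidence intervals beside K-BILD, noting that activity and cylinder use are themselves open to expectation.
- If the baseline oxygen-versus-air walk test is cited, describe it as patient-blinded, not investigator-blinded, evidence of an acute effect only.
- State that the primary conclusion concerns open-label oxygen plus cylinder against none, and that a placebo contribution to K-BILD cannot be excluded.

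This needs no new data, visits or patients. The price is a more modest claim.
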